5.5.9 Emergency breaking of assigned treatment code

Emergency code breaks must only be undertaken when it is required to in order to treat the patient safely. Most often, study treatment discontinuation and knowledge of the possible treatment assignments are sufficient to treat a study patient who presents with an emergency condition. Emergency treatment code breaks are performed using the IRT. When the Investigator contacts the system to break a treatment code for a patient, he/she must provide the requested patient identifying information and confirm the necessity to break the treatment code for the patient. The Investigator will then receive details of the investigational drug treatment for the specified patient and a fax or email confirming this information. The system will automatically inform the Novartis monitor for the site and the Study Team that the code has been broken.

It is the investigator's responsibility to ensure that there is a dependable procedure in place to allow access to the IRT/code break cards at any time in case of emergency. The Investigator will provide:

- protocol number
- study drug name (if available)
- patient number

In addition, oral and written information to the subject/guardian must be provided on how to contact his/her backup in cases of emergency, or when he/she is unavailable, to ensure that un-blinding can be performed at any time.

Study drug must be discontinued in Treatment Period 2 after emergency unblinding.

The possibility to enroll a patient after an emergency break in Treatment Period 2 into an extension study, if available, will be evaluated on a case-by-case basis.

5.6 Study Completion and Discontinuation

5.6.1 Study completion and post-study treatment

A patient will be considered to have completed the study when the patient has received a maximum of 104 weeks of study treatment and completed all of the scheduled study assessment and procedures up to and including the Week 112 visit. All patients who complete the scheduled study assessments and procedures up to and including Week 104 will be eligible to enter an extension trial to continue secukinumab treatment without interruption. Patients who enter the extension study will be considered study completers at Week 104 and the follow-up visit at Week 112 will not be performed.

Information on the subject's completion or premature discontinuation of the study and the reason for discontinuation of the study will be recorded on the appropriate eCRFpage. Additionally, the investigator or site staff must contact the IRT as soon as possible to record the subject's study completion and/or discontinuation.

The Investigator must provide follow-up medical care for all subjects who are prematurely withdrawn from the study, or must refer them for appropriate ongoing care. This care may include initiating another treatment outside of the study as deemed appropriate by the investigator. This treatment may be any non-biologic DMARD. In case of a biologic treatment, a waiting period of 3 months before initiating the treatment is recommended.

5.6.2 Discontinuation of study treatment

The Investigator must discontinue study treatment for a given patient if, on balance, he/she believes that continuation would negatively impact the risk/benefit of trial participation.

Study treatment must be discontinued under the following circumstances:

- Patient/Guardian wish /withdrawal of informed consent
- Pregnancy (see [Section 6.5.7](#) and [Section 7.6](#))
- Use of prohibited treatment as per recommendations in [Table 5-1](#)
- Any situation in which study participation might result in a safety risk to the patient
- Emergence of the following adverse events:
 - Any severe or serious AE that is not compatible with administration of study medication, including AEs that require treatment with an unacceptable co-medication
 - Onset of lymphoproliferative disease or any malignancy except for treated basal cell carcinoma, treated actinic keratoses, treated in situ carcinoma of the cervix or non-invasive malignant colon polyps which are being or have been removed
 - Life-threatening infection
 - Severe hypersensitivity reaction or anaphylactic reaction
- Any laboratory abnormalities that in the judgment of the Investigator are clinically significant and are deemed to place the subject at a safety risk for continuation in the study (A general guidance on clinically notable laboratory values is provided in [Appendix 1](#)).
- Use of any biologic immunomodulating agent except secukinumab
- Any protocol deviation that results in a significant risk to the subject's safety.

If permanent discontinuation of study treatment prior to Week 100 occurs, the patient should NOT be considered withdrawn from the study. The patient should return to the clinic 4 weeks after last study drug administration, for a premature discontinuation visit and 12 weeks after “last study drug administration” for a Post-treatment follow-up visit. Assessments performed at these two visits are detailed in the “premature discontinuation visit” and “Post-treatment follow-up visit” respectively in [Table 6-1](#) and should be completed and recorded in the appropriate eCRF page. The Investigator must determine the primary reason for the patient’s premature discontinuation of study and record this information on the Dosage Administration eCRF page and also contact the IRT to register the patient’s discontinuation from study treatment.

If the patient/guardian cannot or is unwilling to attend any visit(s), the site staff should maintain regular telephone contact with the patient/guardian, or with a person pre-designated by the patient/guardian. This telephone contact should preferably be done according to the study visit schedule.

If study drug discontinuation occurs because treatment code has been broken, please refer to [Section 5.5.9](#).

5.6.3 Withdrawal of informed consent

Patients in consultation with the guardian or the guardian may voluntarily withdraw patient’s consent to participate in the study for any reasons at any time, without being obliged to give any explanation. Withdrawal of consent from the study is defined as when a patient/guardian:

- Does not want to participate in the study anymore
and
- Discontinues all elements outlined in the protocol
and
- Does not want any further visits or assessments
and
- Does not want any further study related contacts
and
- Does not allow analysis of already obtained biologic material

In this situation, the Investigator must make every effort (e.g. telephone, e-mail, letter) to determine the primary reason for the patient/guardian’s decision to withdraw his/her consent and record this information.

Study treatment must be discontinued and no further assessments conducted, and the data that would have been collected at subsequent visits will be considered missing. All biological material that has not been analyzed at the time of withdrawal must not be used.

Further attempts to contact the patient are not allowed unless safety findings require communicating or follow-up.

All efforts should be made to complete the assessments prior to study withdrawal. A final evaluation at the time of the patient's study withdrawal should be made as detailed in [Table 6-1](#).

5.6.4 Loss to follow-up

For subjects whose status is unclear because they fail to appear for study visits without stating an intention to discontinue or withdraw, the Investigator should show "due diligence" by documenting in the source documents steps taken to contact the subject/guardian, e.g. dates of telephone calls, registered letters, etc. A patient cannot be considered as lost to follow-up until the time point of his/her scheduled end of study visit has passed.

5.6.5 Early study termination by the sponsor

The study can be terminated by Novartis at any time for any reason. This may include reasons related to the benefit risk assessment of participating in the study, practical reasons, or for regulatory or medical reasons (including slow enrolment). Should this be necessary, the patient must be seen as soon as possible and treated as a premature subject withdrawal (PSW) (see [Table 6-1](#)). The Investigator may be informed of additional procedures to be followed in order to ensure that adequate consideration is given to the protection of the patient's interests. The Investigator will be responsible for informing the Institutional Review Board/Independent Ethics Committee (IRBs/IECs) of the early termination of the trial.

6 Visit schedule and assessments

[Table 6-1](#) lists all of the assessments and indicates with an "x" or an "s" when the visits are performed. The "x" indicates data collected on the eCRF page, the "s" indicates data collected in the source documents only.

Patients must be seen for all visits on the designated day, or as close to it as possible.

Should a visit be delayed, every attempt should be made to bring the patient back on schedule for the next visit (referring to Baseline visit).

- For visits scheduled through Week 4, the study treatment should not be administered less than 5 days from the previous administration.
- For visits scheduled after Week 4, the study treatment should not be administered less than 14 days from the previous administration, except in case of a flare in Treatment Period 2.

Missed or rescheduled visits should not lead to automatic discontinuation. Patients who prematurely discontinue the study for any reason should be scheduled for a visit 4 weeks after last study drug administration, at which time all of the assessments listed for the Week 104/PSW visit will be performed and a visit 12 weeks after last study drug administration at which time all of the assessments listed for the Week 104/Post-Treatment safety follow up visit will be performed. At this final visit, all dispensed investigational product should be reconciled and the adverse event and concomitant medications reconciled on the eCRF page.

If patients/guardians refuse to return for these assessments or are unable to do so, every effort should be made to contact them or a knowledgeable informant by telephone to determine the reason. Attempts to contact the patient/guardian should be recorded in the source

documentation. Patients/guardians will be contacted for safety evaluations during the 12 weeks following the last administration of study treatment.

In the event of a major health care disruption (e.g., pandemic, epidemic) that limits or prevents on-site study visits, regular phone calls or virtual contacts (every 4 weeks or more frequently, if needed) will occur until the subject can again visit the site. Events qualifying for being reported in the case report form (e.g., AE, procedure) should be entered as appropriate. Special effort should be made to collect information related to TD/PSW visits. If it is not feasible to conduct the TD or the PSW visit on-site, phone calls should be attempted instead.

Screening will be flexible in duration based on the time required to wash out prior anti-rheumatic medications and have duration of up to 8 weeks, during which time, after signature of ICF, the subject be evaluated for eligibility and allowed sufficient time for potential medication washout (see [Table 5-1](#), in addition to all other assessments indicated in [Table 6-1](#)).

Screening will consist of two consecutive visits. During the first screening visit, initial assessments will be performed as outlined in [Table 6-1](#). At that visit the duration of the washout period will be determined. The second screening visit will be performed as follows:

- If the washout period is \leq 4 weeks the investigator should proceed directly to Screening visit 2 on the same day and complete all assessments within the next 4 weeks prior to Baseline.
- If the washout period is more than 4 weeks, the patient/guardian will be instructed to initiate necessary washout regimen and return for Screening visit 2 within 4 weeks prior to Baseline to complete all assessments prior to Baseline.

The rationale is that in all cases screening visit 2 must occur within the 4 weeks prior to Baseline.

All patients evaluated at Screening visits 1 and 2 for eligibility should not be screen failed on the basis of a medication requiring washout, unless the patient will be unable to complete the washout in the appropriate time frame before Baseline.

If for any reason the patient is a screen failure, the patient may be rescreened. There is no restriction on how much time must pass from the date of screen failure and the date of rescreening, but > 1 rescreens must be approved by Novartis on a case by case basis (see also [Section 5.5.1](#)).

For rescreened patients, a new ICF has to be obtained. The date of the new informed consent signature must be entered on the Informed consent CRF page to correspond to the new screening subject number. Informed Consent for a rescreened subject must be obtained prior to performing any study related assessment or collecting any data for the Screening Visit.

For rescreening, all screening assessments must be performed as per protocol, except for the tuberculosis (TB) work up, if applicable, if performed within 12 weeks of Baseline. However, the subject must repeat the QuantiFERON test.

At the discretion of the investigator, laboratory assessments at Baseline visit need not to be performed if screening laboratory assessments were performed within 7 days from Baseline. Urine pregnancy for appropriate female patients and local CRP assessments should be performed at Baseline.

Suggested order of assessments:

Suggested guidelines for conduct of the visit assessments are below:

- Laboratory sample collection, including local CRP sample
- Parent/Guardian/Subject to complete patient reported outcomes (PRO) at the study site prior to any other study assessments.
- Investigator to complete investigator assessments
 - ACR components sent centrally for ACR derivation/flare occurrence - results must be reviewed prior to Week 12/Treatment Period 2 administration of study treatment
- Physical exam (at applicable visits)
- All remaining study visit procedures (e.g. vital signs measurements) must be completed prior to study treatment dosing.
- Contact IRT to register the subject visit, as applicable
- Administration of study treatment, as applicable

Table 6-1 **Assessment schedule**

	Screening ¹		Treatment Period 1							Treatment Period 2 / 3 (Primary Treatment Period) (Note: a patient enters Tx Period 3 in case of flare or when Tx Period 2 completes)							Unscheduled visit	Post-Treatment Safety follow-up	Notes
	1	2	BL	1	2	3	4	8	12/PSW	16 to 20	24	28 to 48	52	56 to 72	76	80 to 100	104 / TD/PSW		
Week	Up to -8	-4 to BL																12 Weeks after last study drug dosed	
																			dose assignment
Vital signs: BP and pulse	X	X	X	X	X	X	X	X	X	X	X	X	X	X	X	X	X	X	
Quantiferon (or PPD skin test if required by local regulation)	X																		Results to be available prior to BL
Hepatitis B, C and HIV serology ³ (only in countries where it is required)	S																		Results to be available prior to BL
ECG	X		X					X				X				X		X	
Contact IRT	S		S	S	S	S	S	S	S	S	S	S	S	S	S	S	S		
Randomization via IRT								X											Only responders will be randomized
Study Drug administration ^{4,5}			X	X	X	X	X	X	X ⁵	X ⁵	X ⁵	X ⁵	X ⁵	X ⁵	X ⁵	X ⁵	X ⁵		If flare confirmed at an unscheduled Tx Period 2 visit, patient will receive Tx Period 3 OL secukinumab and continue to next scheduled visit

6.1 Information to be collected on screening failures

All patients from whom informed consent was obtained but did not enter into the next study period will have the study completion page for the screening period, demographics, inclusion/exclusion, and serious adverse event (SAE) data collected. Adverse events that are not SAEs will be followed by the Investigator and collected only in the source data. Subject may discontinue from the study prior to first study drug administration. These subjects are considered screening failures. All subjects who have signed informed consent and have received the first study drug administration will have all AEs occurring after informed consent is signed recorded on the Adverse Event eCRF page. If a patient discontinued prior to Baseline IRT provider must be notified within 5 days and the reason for patient not being enrolled in Treatment Period 1 will be entered on the screening page disposition CRF page.

6.2 Patient demographics/other baseline characteristics

Subject demographic and baseline characteristic data to be collected on all subjects and recorded in the eCRF include:

- Age, gender, race, ethnicity and source of subject referral.
- Relevant JPsA/ERA JIA and relevant medical history/current medical condition data until the start of study treatment, such as date of diagnosis of JPsA / ERA, previous JPsA / ERA therapies, cardiovascular medical history, smoking history, and surgical history including sterilization for females, if applicable.

Whenever possible, diagnoses and not symptoms will be recorded.

Investigators will have the discretion to record abnormal test findings on the medical history CRF page whenever in their judgment, the test abnormality occurred prior to the informed consent signature.

6.3 Treatment exposure and compliance

All dates and times of study treatment administration will be recorded on the appropriate Dosage Administration Record eCRF page.

Drugs administered prior to start of treatment and other drugs/procedures continuing or started during the study treatment period will be entered in the Prior/Concomitant medications or Significant non-drug therapies eCRF page.

The study treatment will be administered by the study staff directly at the site (except in case of healthcare disruption, such as the COVID-19 pandemic/epidemic-refer to [Section 5.5.4](#)), thus compliance is expected to be 100%, unless temporary interruption is needed for safety reasons as described in [Section 5.5.5](#). Compliance will also be assessed by a Novartis monitor using information provided by the authorized site personnel.

6.4 Efficacy

The efficacy outcome measures used in this study are standard measures used across JIA trials.

- JIA ACR 30, 50, 70, 90 and 100 response criteria

- Physician's Global Assessment of disease activity (VAS)
- Parent's/patient's Global Assessment of subject's overall well-being (VAS included within CHAQ[©])
- Childhood Health Assessment Questionnaire (CHAQ[©])
- Active joint count
- Joint count with limited range of motion
- CRP (local)
- Inactive disease status
- [REDACTED]
- [REDACTED]
- [REDACTED]
- JADAS score
- Total dactylitis count
- Total enthesitis count

All efficacy assessments should be performed prior to administration of study treatment.

6.4.1 JIA ACR response criteria

Standard ACR paediatric Criteria (JIA ACR criteria) consist of 6 core components which will be assessed as scheduled in [Table 6-1](#). JIA ACR 30/50/70/90/100 are defined as 30%, 50%, 70%, 90% and 100% improvement from baseline respectively in a minimum of three variables in the core set with no more than one variable worsening more than 30% as defined in the ACR criteria.

The 6 core set variables are summarized below:

- Physician global assessment of disease activity on a 0 - 100 mm VAS from 0 mm = no disease activity to 100 mm = very severe disease activity
- Parent or patient's (if appropriate in age) Global Assessment of Subject's overall well-being on a 0-100 mm VAS from 0 mm = very well to 100 mm = very poor.
- Functional ability: Childhood Health Assessment Questionnaire (CHAQ[©])
- Number of active joints using the ACR definition (any joint with swelling or in the absence of swelling, limitation of motion accompanied by either pain on motion or tenderness not due to deformity)
- Number of joints with limited range of motion
- Laboratory measure of inflammation: CRP (mg/L)

The respective response variables listed above will be used by a central vendor to determine ACR Pediatric response, responder status at Week 12, and flare occurrence in Treatment Period 2. These results will be communicated to the investigator prior to the patient leaving the study site. Additionally, these components will be used to determine JADAS and inactive disease status (Wallace et al. 2011) as part of secondary [REDACTED] analyses.

6.4.2 Physician's Global Assessment of disease activity (VAS)

The physician will rate the patient's current condition on a 0-100 mm VAS (Appendix 5), ranging from no disease activity (0 mm) to very severe disease activity (100 mm), at each scheduled visit for all patients throughout the study.

Scores on the 100 mm linear scale will be measured to the nearest millimeter from the left. To enhance objectivity, the physician must not be aware of the specific parent's or patient's global assessment of patient's overall well-being, when performing his own assessment on that patient.

6.4.3 Parent's/patient's Global Assessment of subject's overall well-being (VAS)

The parent's or patient's global assessment of the patient's overall well-being will be assessed on the VAS that is part of the CHAQ[®]. The VAS scale ranges from 0-100 mm, from very well (0 mm) to very poor (100 mm).

Scores on the 100 mm linear scale will be measured to the nearest millimeter from the left.

6.4.4 Childhood Health Assessment Questionnaire (CHAQ^{Copyright})

The Childhood Health Assessment Questionnaire, CHAQ[®] (Appendix 6), will be used to assess physical ability and functional status of patients as well as quality of life. The disability dimension consists of multiple choice and VAS items concerning difficulty in performing eight common activities of daily living; dressing and grooming, arising, eating, walking, reaching, personal hygiene, gripping and activities. Subjects choose from four response categories, ranging from 'without any difficulty' to 'unable to do'.

This questionnaire should be completed by the parent (or, for patients 18 years and older, the questionnaire will be completed together by both the patient and parent) according to schedule in Table 6-1. The CHAQ[®] will be completed only in a validated version of the instrument in the language understandable to the parent and/or patient.

Completed questionnaires will be reviewed and examined by the investigator, before the clinical examination, for responses which may indicate potential AEs or SAEs. If AEs or SAEs are confirmed, then the physician must record the events as per instructions given in Section 7.1 and Section 7.2 of the protocol. Investigators should not encourage the patients and/or parents to change the responses reported in the PRO questionnaires.

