Recommended maximum blood collections are in accordance with the 2008 EU Commission Guideline on Ethical Considerations for Clinical Trials on Medicinal Products Conducted with the Pediatric Population. As per the guideline, collections specified in the protocol do not exceed 3% of patients' total blood volume during a 4-week period and/or 1% at any single visit. Patients' total blood volume is estimated at 80 to 90 mL/kg body weight; 3% is 2.4 mL blood per kg body weight, 1% is 0.8 mL blood per kg body weight. The table below outlines the maximum allowable blood volume by weight category. In order to stay within these limits, detailed instructions are provided by the Central Laboratory for all weight categories less than 38 kg.

Table 16-1 Weight range: Recommended maximum blood volume drawn per visit, and per 4 week period

Weight Range Category (kg)	Maximum Allowable Blood Volume Drawn / visit (mL)	Maximum Allowable Blood Volume Drawn / 4 week period (mL)
7-10	5.6	16.8
>10-12	8.0	24.0
>12-14	9.6	28.8
>14-26	11.2	33.6
>26-38	20.8	62.4
>38	30.4	91.2

17 Appendix 5: Physician's global assessment of disease activity (VAS)

The question text below will be shown to and will be answered by the physician. The physician's assessment should be made and recorded without viewing ANY of the patient's assessments. The result of the physician's assessment of the patient's disease activity should be withheld from the patient / parents/guardian so as not to influence his/her own assessment.

The following is the text of the question, but does not represent the final formatting used in the study.

“Considering all the ways ERA/JPsA affects your patient, how would you rate his or her condition today?”

No disease activity	Very severe disease activity
0	100

18 Appendix 6: Childhood Health Assessment Questionnaire (CHAQ)

The following does not represent the final formatting of the CHAQ used in the study.

CHILDHOOD HEALTH ASSESSMENT QUESTIONNAIRE					
1					

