68 GLOBAL EVALUATION: Considering all the ways that arthritis affects your child, rate how he/she is doing by placing a single mark on the line below.					
69 Very well 0 —————— 100 Very poor					

19 Appendix 7: ILAR classification criteria

	Criteria	Exclusions
JPsA (MODIFIED)	Arthritis and psoriasis, or arthritis with two or more of: (a) Dactylitis (b) Nail pitting or onycholysis (c) Psoriasis in a first degree relative	
 • Presence of IgM RF on at least 2 occasions at least 3 months apart • Presence of systemic JIA
ERA	Arthritis and enthesitis, or Arthritis or enthesitis with two or more of: (a) Presence of or history of sacroiliac joint tenderness and/or inflammatory lumbosacral pain (b) HLA-B27 positivity (c) Acute (symptomatic) anterior uveitis (d) History of ankylosing spondylitis, enthesitis related arthritis, sacroiliitis with inflammatory bowel disease, Reiter's syndrome, or acute anterior uveitis in a first-degree relative (e) Onset of arthritis in a boy over the age of 6 years	
 • Psoriasis or in first-degree relative • Presence of IgM RF on at least 2 occasions more than 3 months apart • Presence of systemic JIA

JPsA criteria ([Petty et al 2004](#)) have been modified by removal of the following 2 exclusions: 1) Arthritis in a HLA-B27 positive male beginning after the 6th birthday and 2) diagnosis of ankylosing spondylitis, ERA, sacroiliitis with Inflammatory Bowel Disease (IBD), reactive arthritis (Reiter's syndrome), or acute anterior uveitis, or a history of one of these disorders in a first-degree relative.

20 Appendix 8: ACR definition of flare for JIA

Both criteria 1 and 2 must be fulfilled to meet the definition of a disease flare. Criteria changes described are relative to the End of Treatment Period 1 (Week 12 visit).

1. $\geq 30\%$ worsening in at least 3 of the 6 ACR response variables

- Physician global assessment of overall disease activity
- Parent or patient global assessment of overall well-being
- Functional ability (CHAQ[©])
- Number of joints with active arthritis
- Number of joints with limited range of motion
- Index of inflammation: CRP

2. $\geq 30\%$ improvement in no more than 1 of the 6 ACR response variables

Contingencies:

- if the Physician or Parent Global Assessment is one of the 3 response variables used to define flare, worsening of ≥ 20 mm (1-100mm visual analogue scale) must be present;

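### Section 6.4.4 has the investigator read the completed CHAQ, including the parent/patient global VAS, before the clinical examination, so the masking of the physician global set by 6.4.2 and Appendix 5 is not protected

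*Protocol*

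**What the plan says.** Four places in the Protocol bear on this.

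- **Section 6.4.4 (CHAQ).** "Completed questionnaires will be reviewed and examined by the investigator, before the clinical examination, for responses which may indicate potential AEs or SAEs". The sentence makes no exception for the VAS items.
- **Section 6.4.3 and Appendix 6.** The parent/patient global "will be assessed on the VAS that is part of the CHAQ". The Appendix 6 form ends with that item: "Considering all the ways that arthritis affects your child, rate how he/she is doing by placing a single mark on the line below".
- **Section 6.4.2 and Appendix 5.** For the sake of objectivity, Section 6.4.2 states that "the physician must not be aware of the specific parent's or patient's global assessment of patient's overall well-being" when making the physician's own rating. Appendix 5 goes further: "The physician's assessment should be made and recorded without viewing ANY of the patient's assessments".
- **Section 6, suggested order of assessments.** After laboratory sampling, the patient-reported outcomes come first. Next is "Investigator to complete investigator assessments", and then the physical exam at the visits where it applies. The list has no entry for the review of the questionnaire.

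Appendix 8 (flare), Section 6.4.1 and Appendix 9 (JIA ACR response) use the same six components. Physician global, parent/patient global and CHAQ are three of them.

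**The concern.** The investigator is told to read a form that carries the score to which the rating physician must be masked, and to do so before examining the child. If the same person then scores the physician global, that rating can be drawn towards what the parent has just reported.

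Flare requires worsening in at least three of six components, so the physician global can be the third component beside the two that come from the parent or patient. The same components decide the Week 12 JIA ACR30 response, which is the gate to randomisation and is assessed after open-label treatment. Both globals also enter JADAS. Flare and response are derived centrally from the submitted components, and Section 8.5 requires no adjudication committee, so no later step would restore independence that was lost at the visit.

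**Working it through.** The point rests on wording, so the check sets the passages side by side.

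1. **Is the masked score on the form that is reviewed?** Yes. Section 6.4.3 says so and the Appendix 6 form shows it.
2. **Who reviews the form?** Section 6.4.4 names the investigator. No section requires the reviewer to be someone other than the person who scores the physician global, and none requires the VAS to be covered.
3. **When is it reviewed?** Before the clinical examination, a term the Protocol does not define. There are two readings:
   - *It includes the assessment of joints and disease activity.* The investigator then reads the CHAQ before rating, contrary to 6.4.2 and Appendix 5. The only way to obey every rule would be to rate disease activity before examining the child.
   - *It means only the later physical exam step in Section 6.* The investigator can then rate, read the CHAQ and examine, and every section is met.
4. **Does the visit order choose between them?** No. It is only a suggested order, it has no step for the questionnaire review, and it lists the physical exam only at applicable visits.
5. **How wide is the mask?** Section 6.4.2 covers the parent/patient global. Appendix 5 covers all patient assessments, and so the whole CHAQ. Both apply to the physician global VAS only. Neither mentions joint counts, which Section 6.4.5 assigns to a trained assessor among the site personnel.

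**Design figure, for background.** Section 9.6 gives 33 flares for a hazard ratio of 0.32, 90% power and one-sided 0.025 with 1:1 allocation. Schoenfeld's formula gives 4 × (1.960 + 1.282)² / (ln 0.32)² = 4 × 10.507 / 1.298 = 32.37, rounded up to 33. The target reproduces and is not in question.

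**Can the effect be sized?** Not from the Protocol, which gives no correlation between components and no misclassification rate. An illustration shows how far any answer depends on what is assumed. Let each of the three components have a 10% chance per visit of a spurious threshold crossing, and let parent/patient global and CHAQ correlate at 0.6. The trivariate normal probability that all three cross is then:

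| Correlation of physician global with the other two | All three cross |
|---|---|
| 0.2 | 0.79% |
| 0.4 | 1.38% |
| 0.6 | 2.19% |
| 0.8 | 3.32% |

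A rise to 0.6 multiplies the probability by 2.19 / 0.79 = 2.8 from a start of 0.2, but by only 2.19 / 1.38 = 1.6 from a start of 0.4. Every input is assumed. The table shows direction only and also omits the flare criterion that limits improving components.

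**The case against.** The strongest defence is that the Protocol already states the mask twice, in specific and mandatory terms, while 6.4.4 is a general sentence about detecting adverse events and does not waive it. The suggested order puts the investigator's assessments ahead of the physical exam, so a site can comply with every section, as it also can if a non-rater reads the form. This stands, and it limits the point: independence is unprotected, but it is not shown to be lost. It does not remove the point, because the most direct reading of 6.4.4 breaks the mask and no text requires the compliant sequence.

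A reader might infer more than the documents support:

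- *That the instructions can never both be followed.* They can, by either route just described.
- *That the joint counts are compromised too.* The masking rules do not cover them, and the joint assessor need not be the investigator.
- *That one bad parent report yields a flare.* Under Appendix 8 a global used for flare must worsen by at least 20 mm as well as 30%, and no more than one component may improve by 30% or more. That three subjective components can suffice is a property of the flare definition and does not come from 6.4.4.
- *That the treatment comparison is biased.* Treatment Period 2 is double-blind, so the review affects both arms alike. No false treatment effect or inflated type I error follows.
- *That flares are inflated by a stated factor.* Some correlation is expected anyway, because both raters are scoring the same child's disease.

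**Conclusion.** The conflict holds on the direct reading of 6.4.4 against 6.4.2 and Appendix 5, and the visit order does not resolve it. What follows is that the physician global, one of six components of the primary endpoint and of the Week 12 responder decision, lacks a procedural safeguard for a masking rule the Protocol itself sets.

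The possible harm is correlated components and some misclassified flares or responses. In Treatment Period 2 this would be non-differential, and its size cannot be calculated from the documents. The conclusion assumes that at some sites the investigator who reviews the questionnaire also scores the physician global, which the Protocol permits. The 33-event target is unaffected. The point merits correction because the remedy is nearly free, not because a large effect has been shown.

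**What to change.** In Section 6.4.4, change the timing of the review so that it takes place *after the physician's global assessment has been recorded and before study treatment is administered*. Alternatively, allow existing site staff who do not score the physician global to do the adverse event check. Add the same step to the order of assessments in Section 6.

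The limit of before dosing matters. Asking only that the review happen before the patient leaves would allow it to follow the injection, contrary to Section 5.5.4 (visit assessments completed before administration) and Section 6.5 (safety assessments before treatment).

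Recording the joint counts before the review as well is a reasonable option, but it would extend the present rules.

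The cost is one sentence in 6.4.4 and one line in Section 6, with no added staff, visit or procedure. The adverse event check stays within the same visit.
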